#### 3.3 Pharmacokinetic analysis set

PK analysis set includes all participants in the safety analysis set and have baseline and at least one post-baseline evaluable data point. PK analysis set will be used for PK and ADA analyses.

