#### **4.7 Pharmacokinetic (PK) Variables**

The blood samples will be collected at day 1/baseline (pre-dose and EOI), days 8, 15 (pre-dose and EOI), 29 (pre-dose and EOI), 43, 57, 85, 113/EOT, 141, and 169/EOS.

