#### **4.8 Pharmacodynamic (PD) Variables**

## 4.9 Immunogenicity Variable

The variables include ADA status (positive or negative) as follows:

- Total participants negative in the ADA assay at all time points analyzed
- Total participants positive in the ADA assay at any time point analyzed
- Total participants with pre-existing ADA
- Total participants with treatment emergent response
- Total participants with treatment boosted response
  - *Pre-existing ADA*: Either an ADA positive response in the assay at baseline with all post first dose ADA results negative, OR a positive response at baseline with all post first dose ADA responses less than 4-fold over baseline titer levels.
  - *Treatment-boosted response*: Pre-existing ADA that is increased to a higher concentration (4-fold or higher level) after administration of therapeutic protein product.
  - *Treatment-emergent response*: ADA developed de novo (seroconversion) following administration of therapeutic protein product in a participant who lacked detectable pre-existing ADA
    - a. *Persistent response*: Treatment-emergent response detected at 2 or more sampling time points during the treatment (including follow-up period if any), where the first and last ADA-positive samples (irrespective of any negative samples in between) are separated by a period of 16 weeks or longer.

- b. *Indeterminate Response*: Treatment-emergent response with only the last collected sample positive in the ADA assay
- c. *Transient response*: Treatment emergent ADA positive assay response that is not considered persistent or indeterminate.

Blood sample for the immunogenicity analysis will be collected at Day 1/Baseline (pre-dose), days 15(pre-dose), 29 (pre-dose), 43, 57, 85, 113/EOT, 141, and 169/EOS.

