### 5.8.3 Analysis of Vital Signs

Summaries of vital sign variables will include:

- Descriptive statistics of vital sign variables and change from baseline by treatment and visits/timepoints
- Notable findings in vital signs will be summarized by treatment and visit/timepoint, which are defined as,
  - Temperature:  $>39.0$  degrees
  - An increase in Pulse Rate from baseline by  $\geq 25\%$  for on-treatment values  $>100$  beats/min
  - A decrease in Pulse Rate from baseline by  $\geq 25\%$  for on-treatment values  $<50$  beats/min.
  - Systolic BP  $\geq 140$  mmHg and increase by 20 mm Hg.
  - Diastolic BP  $\geq 90$  mmHg and increase by 10 mm Hg.
  - Systolic BP  $\leq 80$  mmHg and decrease by 20 mm Hg.
  - Diastolic BP  $\leq 50$  mmHg and decrease by 10 mm Hg.

All the above tables will be presented through the Week 36 visit.

A listing of vital signs data will be provided for each participant by treatment and visit.

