### 5.9 Analysis of Pharmacokinetic Data

Descriptive summary tables (geometric mean, arithmetic mean, minimum, maximum, SD, and % coefficient of variation etc.) will be presented for the below categories by visit.

- Serum concentration for each treatment group
- PK concentration in ADA positive and ADA negative participants by treatment group
- Dose adjusted PK concentration in ADA positive and ADA negative participants

Following figures will be provided for the serum concentration data,

- Mean ( $\pm$ SD) serum concentration vs time profile: Linear scale
- Mean ( $\pm$ SD) serum concentration vs time profile: Semi-log scale
- Individual serum concentrations vs time profile: Linear scale
- Individual serum concentrations vs time profile: Semi-log scale

Serum concentration will be listed for each participant by treatment and visit.

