### 6.1 Definition of Baseline for Efficacy/Safety Variables

Unless otherwise specified, the baseline assessment for all measurements will be the latest available valid measurement taken prior to the administration of study drug (Week 0 (Day 1)).

When it is not possible to determine the time of assessment, baseline value would be determined based on the measurement recorded on the day administration of the first dose of IMP.

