## 6.3 Analysis Visit Window

For summaries that include data collected over multiple visits, where appropriate, the data will be summarized by analysis visit window. If there are multiple measurements within a scheduled visit window (refer [Appendix 11.3](#)), the closest measurement to the scheduled timepoint of the visit will be used in the analysis. If there are two observations which have the same difference in days to the planned day, but which are not measured on the same day, the later value will be selected. If there is more than one observation on the same day, then;

- Latest value will be considered in all cases except for vital signs, ECG.
- Average value will be considered in cases of vital signs and continuous ECG values.
- The worst value will be considered for ECG interpretation.

[figure not shown]
For PK and ADA data, if multiple measurements are taken within a scheduled visit window, the earliest value will be used for the analysis.

All measurements will be presented in the listing.

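### Taken literally, the SAP's visit-window rules leave the end-of-infusion samples out of the by-visit PK tables; separately, they file pre-dose PK and ADA samples of a third dose given on Days 37–39 under Week 6

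*SAP*

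**What the plan says.** **Sampling.** SAP 4.7 schedules PK samples at "day 1/baseline (pre-dose and EOI), days 8, 15 (pre-dose and EOI), 29 (pre-dose and EOI", then once each on Days 43, 57, 85, 113, 141 and 169. SAP 4.9 schedules ADA samples before dosing on Day 1 and then on "days 15(pre-dose), 29 (pre-dose), 43, 57, 85, 113/EOT, 141, and 169/EOS". Protocol 7.4, Table 5, gives the same days, has separate rows for pre-dose and EOI, and describes the Day 43 and Day 57 samples as 14 and 28 days after the third dose.

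**Selection.** SAP 6.3 reads: "For PK and ADA data, if multiple measurements are taken within a scheduled visit window, the earliest value will be used for the analysis". For most other data, the same section takes the latest of several same-day values; for vital signs and continuous ECG values it takes the average.

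**Windows.** SAP 11.3 puts PK in Group 1 and ADA in Group 2. Both groups define Week 4 as Days 26–36, Week 6 as Days 37–50 and Week 8 as Days 51–71. Neither separates pre-dose from EOI. Group 7, for study treatment administration, defines Week 4 as any day after Day 25.

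**Tables.** Under SAP 5.9 the concentration summaries "will be presented for the below categories by visit". For vital signs, SAP 5.8.3 goes a level lower: "Descriptive statistics of vital sign variables and change from baseline by treatment and visits/timepoints".

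**Dosing.** Protocol 6.5 and the schedule footnotes in both documents allow the Week 4 dose up to 10 days after its allocated day.

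**The concern.** There are two separate issues.

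First, on a dosing day the plan collects a trough and a near-peak concentration about an hour apart. A rule that keeps one value per study-day window cannot show both. As worded, it keeps the trough. The by-visit tables, including those that compare ADA-positive with ADA-negative participants, would then hold no EOI concentration for any of the three infusions. If a pre-dose sample were missing, the EOI value would be the earliest in its window and would be averaged with other participants' troughs.

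Second, the dose and its own samples can be filed under different weeks. A third dose on Days 37–39 belongs to Week 4 in Group 7, but the PK and ADA samples drawn just before it belong to Week 6 in Groups 1 and 2. A concentration or ADA result from before the third dose would then appear where the reader expects one from after it.

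The PK profile and immunogenicity are exploratory objectives (SAP 1.2.3). What is at stake is the accuracy of those descriptive tables.

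**Working it through.** **Step 1: count the samples (SAP 4.7 and 4.9; protocol Table 5 agrees).**
- PK: 2 on each of Days 1, 15 and 29, plus one each on Days 8, 43, 57, 85, 113, 141 and 169. That is 3 × 2 + 7 = 13, of which 3 are EOI.
- ADA: one each on Days 1, 15, 29, 43, 57, 85, 113, 141 and 169 = 9, none at EOI.

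**Step 2: apply the windows and the earliest-value rule on the nominal schedule.**
- PK has 10 windows from Baseline to Week 24, and each is filled. 13 − 10 = 3 samples are left out, namely the EOI samples of Days 1, 15 and 29: 3/13 = 23%.
- ADA has 9 windows (no Week 1), and all 9 samples are used.
- The general same-day rule would not help. Taking the latest value would keep EOI and drop the pre-dose sample.

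**Step 3: a missing pre-dose sample.**
- On Day 15 or Day 29 the EOI sample becomes the earliest value in its window and enters the trough row.
- Day 1 is different. SAP 6.1 says "the baseline assessment for all measurements will be the latest available valid measurement taken prior to the administration of study drug", so an EOI sample cannot be baseline. SAP 3.3 says "PK analysis set includes all participants in the safety analysis set and have baseline and at least one post-baseline evaluable data point", so a participant without a baseline value is outside the PK set.

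**Step 4: permitted dose days against the windows.**
- Second dose: latest day 15 + 5 = Day 20, inside Week 2 (Days 12–25 for PK, 2–25 for ADA). There is no gap.
- Third dose: latest day 29 + 10 = Day 39, but Week 4 closes on Day 36. The ordinary visit window ends on 29 + 3 = Day 32, so the permitted late days are 33–39 (7 days). Days 37–39 (3 days) fall in Week 6.

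**Step 5: third dose on Days 37–39, other samples on their scheduled days unless stated.** In each case the Week 6 value is the third dose's pre-dose sample.
- *Week 6 visit stays near Day 43, no sample at the scheduled Week 4 visit.* Week 4 is empty and the Day 43 sample is displaced. PK: 9 of 10 windows filled, so 9 of 13 samples used. ADA: 8 of 9.
- *As above, but a sample was also taken on Day 29.* This is possible after a dose interruption, but not when the visit itself was late. All 10 PK and 9 ADA windows are filled, but Day 43 is still displaced.
- *Week 6 sample follows the dose by 14 days.* 37 + 14 = 51 and 39 + 14 = 53, so it falls on Days 51–53, inside Week 8. As the earliest value there it displaces the Day 57 sample. Without a Day 29 sample, Week 4 is again empty, with PK at 9 of 13 and ADA at 8 of 9.

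For a third dose on Days 26–36, sampled only at the dosing visit, the result is that of Step 2.

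**The case against.** **The earliest-value rule may not be meant for planned timepoints.** This is the strongest argument. SAP 6.3 averages same-day vital signs, yet 5.8.3 reports them by timepoint within the visit. Both can hold only if the 6.3 tie-breaks act within a nominal timepoint. SAP 4.7 and Table 5 list pre-dose and EOI separately, and 6.3 applies visit windows only where appropriate. A reader might infer that the plan has decided to discard EOI values. The documents do not support that, and the loss is conditional on a literal reading. What remains is that neither 5.9 nor 6.3 gives PK the timepoint level that 5.8.3 gives vital signs. Mock shells, which SAP section 5 mentions and which are not among the documents, may settle it.

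**Little is lost.** This stands. Listings keep every sample. SAP 5.9 also plans figures such as "Individual serum concentrations vs time profile: Linear scale", which are not stated to be limited to one value per window, and population PK is separate. A reader might infer that peak exposure goes unreported; only the by-visit tables are in question.

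**The late dose may never have occurred.** Also fair. The SAP's authors widened Week 2 for unscheduled assessments but left Week 4 alone, which may mean that no late third dose needed room. Three days of seven is a count of calendar days, not a frequency.

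**Windowing samples by study day is a legitimate convention.** It is, but here it puts a dose and its own pre-dose samples in different weeks.

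**The Day 43 sample need not be the one displaced.** Correct. A reader might infer that it always is, but that requires the Week 6 visit to stay near Day 43.

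**Conclusion.** Both parts hold, with different force, and the severity is minor.

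Part 1 is a gap in wording. If SAP 6.3, 11.3 and 5.9 are applied literally, 3 of 13 PK samples per participant (23%) are absent from the by-visit tables, and a missing Day 15 or Day 29 pre-dose sample puts an EOI value among troughs. If the rule covers only repeats of one timepoint, neither happens.

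Part 2 does not depend on that reading. For a third dose on Days 37–39, the Week 6 PK and ADA values come from before the dose, and Week 4 is empty unless the participant was also sampled at the scheduled visit. One later sample is displaced: Day 43 if the Week 6 visit was not moved, Day 57 if it followed the dose by 14 days. This assumes that the 10 days run from Day 29. The number of participants affected is unknown and may be none.

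The primary and secondary endpoints are unaffected, and the dosing-delay allowance is not in question. The analysis windows need to be reconciled with it.

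**What to change.** - **SAP 5.9 and 6.3:** summarise PK concentrations by nominal visit and timepoint (pre-dose or EOI), and limit the earliest-value rule to repeat samples of the same nominal timepoint.
- **SAP 11.3:** from the third dose onward, assign PK and ADA samples by nominal visit and dose-relative timepoint as in protocol Table 5, not by study day alone. This reconciles Groups 1 and 2 with Group 7 and with the permitted delay. Reassigning only the samples of the third-dose visit would not be enough: a Week 6 sample taken on Days 51–53 would still displace Day 57.

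With both changes, all 13 PK and all 9 ADA scheduled samples have a place in the summaries, against 10 and 9 on the nominal schedule read literally, and 9 and 8 after a third dose on Days 37–39 with no sample at the scheduled Week 4 visit. The cost is about three sentences in the SAP, with matching table shells, and no new data.

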## 7. PLANNED ANALYSES

### 7.1 Interim Analysis

#### 7.1.1 Interim Analyses Outputs

### TEAE

- Overall summary of TEAE
- Summary of TEAEs by SOC and PT
- Summary of Serious TEAEs by SOC and PT
- Summary of TEAEs occurring for  $\geq 2$  participants in any of the treatment group by SOC and PT
- Summary of TEAEs by PT and maximum severity
- Summary of TEAEs with CTCAE grade 3 or higher by PT
- Summary of treatment related TEAEs by SOC and PT

### Lab values

- Descriptive statistics of continuous laboratory result and change from baseline by visit in hematology and chemistry parameters
- Number (n) and percentage (%) of participants with CTCAE grade for key hematology parameters (WBC, neutrophils, lymphocytes, platelet, and hemoglobin)
- Number (n) and percentage (%) of participants with CTCAE grade for key serum chemistry parameters (ALT, AST, serum creatinine, and bilirubin)

### Vital signs

- Proportion of participants with notable findings in vital signs

### ECG

- Proportion of participants with notable findings in ECG

### IHC results

- Listing of OX40 positive cells (cells/mm^2) in biopsy by visit for individual and for each dose group
- Listing of OX40L positive cells (cells/mm^2) in biopsy by visit for individual and for each dose group

- Listing of Tryptase positive cells (cells/mm^2) in biopsy by visit for individual and for each dose group
- Listing of CD3 positive cells (cells/mm^2) in biopsy by visit for individual and for each dose group
- Listing of CD8 positive cells (cells/mm^2) in biopsy by visit for individual and for each dose group
- Listing of FcEpsilonR1 positive cells (cells/mm^2) in biopsy by visit for individual and for each dose group
- Listing of KRT35 staining results in biopsy by visit for individual and for each dose group
- Listing of H&E staining results in biopsy by visit for individual and for each dose group

## 7.2 Final Analysis

## 8. SAFETY REVIEW COMMITTEE

A safety review committee (SRC) consisting of three independent physicians will be convened to review safety data, dose escalation criteria, and the study stopping criteria.

SRC analysis outputs will be prepared as outlined in the document '*Statistical Considerations for the SRC Analysis of IMG-007-202 Data*' dated 11Apr2024. The list of SRC outputs is given in the [Appendix 11.5](#).

## 9. SOFTWARE

All analyses will be done using SAS Version 9.4 or above.

## 11. APPENDIX

## 11.1 Schedule of Assessments

Procedures	Screening	Treatment Period								Follow-up Period		Extended Follow-up Period post EOS			
		Baseline	V2	V3	V4	V5	V6	V7	V8	EOT 	EOS 	V10	V11	V12	V13
Visit	V1	Week 0	Week 1	Week 2	Week 4	Week 6	Week 8	Week 12	Week 16	Week 20	Week 24	Week 30	Week 36		
		Day -35 to -1	Day 1	Day 8	Day 15	Day 29	Day 43	Day 57	Day 85	Day 113	Day 141	Day 169	Day 211	Day 253	
		Time window			± 3d	± 3d	± 3d	± 3d	± 3d	± 3d	± 3d	± 3d	± 7d	± 7d	

1. Study-specific procedures will be performed after receipt of signed informed consent.
2. Medical history includes prior/concurrent relevant conditions and medications, prior/current AA treatment, and surgical history. At the Baseline (Day 1) visit, medical history is updated prior to administration of study treatment. Demographics include year of birth, gender, race and ethnicity, height, and body weight. BMI will be calculated as weight (kg) / [height (m) x height (m)].
3. Vital signs include blood pressure, pulse, respiratory rate and body temperature. On study treatment dosing days, i.e., Baseline (Day 1), Week 2 (Day 15), and Week 4 (Day 29), vital signs should be assessed before initiation of infusion; 15 (± 5) minutes after the initiation of the infusion; 15 (± 5) minutes after EOI, and 1 hour (± 15 minutes) post EOI. Participants need to rest for 5 minutes before having their vital signs measured.
4. Physical examination: A full physical examination will be performed at Screening. A brief physical examination will be completed at the Baseline visit, and symptom-directed physical examinations will be completed at each follow-up (including the extended follow-up) visit at the discretion of the investigator.
5. Laboratory assessments will be analyzed at a central laboratory. If lab test results do not meet the inclusion/exclusion criteria at Screening, a repeat test may be performed. The sample should be taken before dosing on dosing days.
6. All participants will undergo TB test (QuantiFERON-TB Gold [QFT-G] test or an equivalent test) at Screening. Participants who receive study treatment will be followed up by a TB risk assessment questionnaire at Week 16 (Day 113)/EOI, Week 24 (Day 169)/EOS and Week 36 (Day 253). If the participants have a negative TB test at the initial screening evaluation, the TB test could be waived at the rescreening if no changes in the participant's medical history that warrant retesting, and no more than 90 days have passed.
7. Viral disease screening includes HBsAg, HBsAb, HBcAb, HCV antibody and HIV antibody.
8. Pregnancy tests are only for women who are of childbearing potential. Serum hCG will be performed at the Screening, Baseline (Day 1), Week 2 (Day 15), Week 4 (Day 29) visits, and at the selected follow-up (including the extended follow-up) visits. In addition, a urine pregnancy test must be performed prior to dosing at the Baseline (Day 1), Week 2 (Day 15), and Week 4 (Day 29) visits, which will be conducted at the study site.
9. On dosing days, study treatment will be administered as an IV infusion over approximately 60 minutes with a slower rate during the first 15 minutes. Participants will be closely monitored at the study site for a minimum of 1 hour after completion of each infusion or until any AEs observed have resolved or stabilized, whichever is longer. For diagnostic purposes, any participant who experiences any systemic infusion-related event should have a blood sample taken, ideally 30–60 minutes after the onset, for tryptase testing, and samples should be analyzed by a local laboratory if feasible. Study sites should have access to equipment or facilities for the management of potential hypersensitivity reactions. On dosing days, study treatment infusion should be performed after other study assessments have been performed. If a dose is not administered on schedule due to a visit occurring beyond the visit window specified or due to dose interruption for reasons stated in [Section 6.10.1.2](#) of protocol, the dose may be administered if it is no later than 5 days after the allocated visit day (a 10-day delay will be allowed for the last dose at Week 4) specified. Otherwise, the dose will be considered missed, and dosing will resume with the next scheduled dose. The study site will contact the participants by telephone approximately 24 hours after the infusion for general AE query.

10. SALT, IATS, IGA-EB, IGA-EL, IGA-FN should be performed only by adequately trained investigators or sub-investigators. Efforts should be made that the same assessor performs the assessments of a particular participant throughout the study. IGA-EB, IGA-EL, IGA-FN will only be performed in participants with AA on eyebrows, eyelashes and/or nails.
11. Participants will complete the questionnaire for PGIS-AA, PGIS-S, PGIS-EB, PGIS-EL and PGIS-FN. PGIS-EB, PGIS-EL and PGIS-FN will only be performed in participants with AA on eyebrows, eyelashes and/or nails.
12. Participants will complete the AAPPO questionnaire to measure hair loss, emotional symptoms, and activity limitations over the past week.
13. Participants will complete the HADS to assess states of anxiety and depression over the past week.
14. Participants will complete the questionnaires for PGIC-AA, PGIC-S, PGIC-EB, PGIC-EL and PGIC-FN. PGIC-EB, PGIC-EL and PGIC-FN will only be performed in participants with AA on eyebrows, eyelashes and/or nails.
15. On dosing days, blood sample should be taken within 60 minutes before dosing and within 10 minutes after end of infusion.
16. On dosing days, blood sample should be taken within 60 minutes before dosing.

[REDACTED]

[REDACTED]

[REDACTED]

[REDACTED]

21. Participants who discontinue treatment early (before completing the 4-week dosing period) should continue with all the remaining study visits. Participants who withdraw from the study any time before the Week 16 visit should complete the Week 16 (Day 113)/EOT visit at withdrawal. Participants who withdraw from study early during the follow-up period should complete the Week 24 (Day 169)/EOS visit at withdrawal. Participants who discontinue early after the Week 24/EOS visit but before the Week 36 visit should complete Week 36 (Day 253) visit at withdrawal.

Abbreviations: AA = alopecia areata; ADA = anti-drug antibody; AAPPO= alopecia areata patient priority outcomes; AE = adverse event; BMI = body mass index; ECG = electrocardiogram; EOI = end of infusion; EOS = end of study; EOT = end of treatment; HADS= hospital anxiety and depression scale; HBcAb = antibody to hepatitis B core antibody; HBsAb= hepatitis B surface antibody; HBsAg= hepatitis B surface antigen; hCG = human chorionic gonadotropin; HCV = hepatitis C virus; HIV = human immunodeficiency virus; IATS = investigator's assessment of a target scalp lesion; IGA-EB = investigator's global assessment of eyebrows; IGA-EL = investigator's global assessment of eyelashes; IGA-FN = investigator's global assessment of fingernails; IgE = immunoglobulin E; IV = intravenous; PD = pharmacodynamic; PGIC-AA = patient's global impression of change of alopecia areata; PGIC-EB = patient's global impression of change of alopecia areata on eyebrows; PGIC-EL = patient's global impression of change of alopecia areata on eyelashes; PGIC-FN = patient's global impression of change of alopecia areata on fingernails; PGIC-S= patient's global impression of change of alopecia areata on scalp; PGIS-AA = patient's global impression of severity of alopecia areata; PGIS- EB = patient's global impression of severity of alopecia areata on eyebrows; PGIS- EL = patient's global impression of severity of alopecia areata on eyelashes; PGIS-FN = patient's global impression of severity of alopecia areata on fingernails; PGIS-S = patient's global impression of severity of alopecia areata on scalp; PK = pharmacokinetic; S = serum; SALT= severity of alopecia tool; TB = tuberculosis; U = urine; V = visit; WCBP = women of childbearing potential

